6.2. Secondary Endpoints

6.2.1. ISGA Success based on Central Readers Assessment

- Estimand strategy: composite, Estimand 2 ([Section 2.1.2](#))
- Analysis set: FAS ([Section 4](#))
- Variable: ISGA success at Weeks 1-6 based on Central Readers digital images assessment
- Analysis method: Normal approximation to binomial
- Intercurrent event: A participant with a missing observation or after an intercurrent event of discontinuation of treatment will be considered a non-responder for the visit of interest.
- P-value from normal approximation test, the estimate of proportion, difference in proportion and the corresponding 90% CI of participants with response at each visit between crisaborole ointment, 2% versus vehicle will be presented. Proportions of response (\pm SE) will also be presented graphically by treatment group.

6.2.2. ISGA Success at Week 6/EOT based on In-person Assessment

- Estimand strategy: while-on-treatment, Estimand 1 ([Section 2.1.2](#))
- Analysis set: FAS ([Section 4](#))
- Variable: ISGA success at Week 6/EOT based on in-person assessment
- Analysis method: Normal approximation to binomial
- Intercurrent event: all data after an intercurrent event of discontinuation of study intervention will be excluded, data at Week 6 or EOT will be included;
- P-value from normal approximation test, the estimate of proportion, difference in proportion and the corresponding 90% CI of participants with response at Week 6/EOT between crisaborole ointment, 2% versus vehicle will be presented. Proportions of response (\pm SE) will also be presented graphically by treatment group.

6.2.3. ISGA Score of Clear or Almost Clear based on Central Readers Assessment

- Estimand strategy: composite, Estimand 2 ([Section 2.1.2](#))
- Analysis set: FAS ([Section 4](#))
- Variable: ISGA clear or almost clear at Weeks 1-6 based on Central Readers digital images assessment

- Analysis method: Normal approximation to binomial
- Intercurrent event: A participant with a missing observation or after an intercurrent event of discontinuation of treatment will be considered a non-responder for the visit of interest.
- P-value from normal approximation test, the estimate of proportion, difference in proportion and the corresponding 90% CI of participants with response at each visit between crisaborole ointment, 2% versus vehicle will be presented.

6.2.4. ISGA Score of Clear or Almost Clear based on In-person Assessment

- Estimand strategy: while-on-treatment, Estimand 1 ([Section 2.1.2](#))
- Analysis set: FAS ([Section 4](#))
- Variable: ISGA clear or almost clear at Week 6/EOT based on in-person assessment
- Analysis method: Normal approximation to binomial
- Intercurrent event: all data after an intercurrent event of discontinuation of study intervention will be excluded, data at Week 6 or EOT will be included
- P-value from normal approximation test, the estimate of proportion, difference in proportion and the corresponding 90% CI of participants with response at Week 6/EOT between crisaborole ointment, 2% versus vehicle will be presented.

6.2.5. Percentage Change from Baseline in TSS at Weeks 1-6 based on Central Readers Assessments

- Estimand strategy: hypothetical, Estimand 3 ([Section 2.1.2](#))
- Analysis set: FAS ([Section 4](#))
- Variable: Percent change from baseline to Weeks 1-6 in TSS based on central readers assessment
- Analysis method: MMRM in [Section 5.2.1](#)
- Intercurrent event: All data after an intercurrent event (eg, discontinuation of treatment), if collected, will be excluded;
- The LSM along with the corresponding SE for each treatment group, LSM difference along with the corresponding SE, 90% CI, and p-value will be presented. LSM (\pm SE) will also be presented graphically by treatment group.

6.2.6. Percent Change from Baseline in Lesional %BSA based on In-person Assessment

- Estimand strategy: while-on-treatment, Estimand 1 ([Section 2.1.2](#))
- Analysis set: FAS ([Section 4](#))
- Variable: Percent change from baseline to Week 6/EOT in %BSA based on in-person assessment
- Analysis method: ANOVA in [Section 5.2.1](#)
- Intercurrent event: All data after an intercurrent event (eg, discontinuation of treatment), if collected, will be excluded, data at Week 6 or EOT will be included.
- The LSM along with the corresponding SE for each treatment group, LSM difference along with the corresponding SE, 90% CI, and p-value will be presented.

6.2.7. Percent Change from Baseline in Lesional %BSA based on Central Readers Assessment

- Estimand strategy: hypothetical, Estimand 3 ([Section 2.1.2](#))
- Analysis set: FAS ([Section 4](#))
- Variable: Percent change from baseline to Week 1- 6 in %BSA based on Central Readers digital images assessment
- Analysis method: MMRM in [Section 5.2.1](#)
- Intercurrent event: All data after an intercurrent event (eg, discontinuation of treatment), if collected, will be excluded.
- The LSM along with the corresponding SE and 90% CI for each treatment group, LSM difference along with the corresponding SE, 90% CI, and p-value will be presented.

CCI

6.4. Subset Analyses

Percentage change from baseline in TSS, ISGA success, ISGA clear/almost based on HVP in-person assessment will be analyzed by subgroups of type of standard of care, skin type, baseline ISGA, disease duration (by median), age (≤ 64 vs ≥ 65), race (White vs Non-white).

6.5. Baseline and Other Summaries and Analyses

6.5.1. Baseline Summaries

Demographics and baseline characteristics listed in Section 3.4 will be summarized according to Pfizer standards.

6.5.2. Study Conduct and Participant Disposition

Participants evaluation, disposition, discontinuation will be summarized according to Pfizer standards.

6.5.3. Study Intervention Compliance

Participant compliance with study intervention will be assessed by Investigator (or designee) review of eDiary responses.

A participant will be considered compliant with the dosing regimen if he/she receive 80% to 120% of the expected number of doses, in accordance with the protocol.

The number and percentage of participants who are compliant with the dosing regimen, number of dosing days and number of applications, and total amount of intervention used will be summarized according to Pfizer standards.

6.5.4. Concomitant Medications and Non-drug Treatments

Any medication (including over-the-counter or prescription medicines, vitamins, and/or herbal supplements), vaccine or non-medication therapies that the participant is receiving at the time of enrollment or receives during the study must be recorded at all study visits/contacts.

All concomitant medications taken during the study must be recorded in study records with indication, reference to any associated adverse event, dose, and start and stop dates of administration.

The Pfizer Medical Monitor should be consulted if there are any questions regarding concomitant or prior therapy for SD prior to determining participant eligibility.

Prior drug and non-drug treatment, concomitant drug and non-drug treatment will be summarized according to Pfizer standards. The summary will be performed by treatment group for overall and separated by SD and non-SD treatments.

6.6. Safety Summaries and Analyses

Safety analyses will be summarized in accordance with Pfizer Data Standards.

All clinical AEs, SAEs, TEAEs, withdrawal due to AEs, will be reviewed and summarized on an ongoing basis during the study to evaluate the safety of participants.

Safety data will be presented in tabular and/or graphical format and summarized descriptively, where appropriate. All safety endpoints will be listed and summarized in accordance with Pfizer Standards. Categorical outcomes (eg, AEs) will be summarized by participant counts and percentage. Continuous outcome (eg, pulse rate, etc) will be summarized using n, mean, median, standard deviation, etc. Participant listings will be produced for these safety endpoints accordingly.

6.6.1. Adverse Events

The safety data will be summarized in accordance with Pfizer Data Standards. All safety data will be summarized descriptively through appropriate data tabulations, descriptive statistics, categorical summaries, and graphical presentations. Safety endpoints for the study include:

- Treatment-emergent AEs and SAEs;
- Withdrawals from treatment/study due to AEs.

6.6.2. Laboratory Data

Laboratory data will be listed.

6.6.3. Physical Examination

Physical examination data will be listed.

7. INTERIM ANALYSES

An IA may be performed to assess efficacy after approximately 50 participants complete 6 weeks treatment or early discontinue study intervention. Interim analysis results will be used for decisions regarding stopping for futility and planning for future studies.

All study personnel and sponsor's staff involved with this study will remain blinded to individual subject data for interim analysis.

A third party Pfizer programmer/biostatistician who is unrelated to the study team will conduct the interim analysis. The third party will receive the unblinded treatment codes from clinical pharmacy and make the appropriate changes to the analysis programs prepared by the clinical programmer and study biostatistician in the **CCI** [REDACTED]. After successful execution of

all interim analysis programs, the third party will place the results in **CCI**. An **CCI** folder containing summary data will be created and protected such that only designated persons can gain access.

The decision criterion is based on the primary endpoint. The efficacy will not be claimed based on this interim analysis. If the efficacy criterion is met, the study will continue and remain blinded to study personnel until the final database unblinding, and phase 3 studies can start planning. The final analysis will be performed at the final official database release. If futility criterion is met, this study will be terminated.

7.1.1. Data Monitoring Committee

This study will not use a data monitoring committee. However, if an IA is performed, an IRC will be established to review the interim analysis results and make the decision for this study and crisaborole stasis dermatitis project.

8. REFERENCES

None.

9. APPENDICES

Appendix 1. Summary of Efficacy Analyses

Endpoint	Analysis Type	Population	Data Inclusion and Rules for Handling Intercurrent Events and Missing Data	Analysis Model
Percent Change from baseline to Week 6/EOT in TSS based on HVP in-person assessment	Summary	FAS	observed data	N/A
	Main analysis	FAS	The data after an intercurrent event, if collected, will be excluded, data at Week 6 or EOT (within date of last dose +10 days) will be included.	ANOVA with term treatment
	Sensitivity analysis	FAS	The data after an intercurrent event, if collected, will be excluded, observed cases at	ANOVA with term treatment

			Week 6 will be included. No imputation for missing data.	
	Sensitivity analysis	FAS	The data after an intercurrent event, if collected, will be excluded, observed cases at Week 6 will be included. Missing data at Week 6 will be derived for the analysis using the method of multiple imputation.	ANOVA with term treatment
Percent Change from baseline to Weeks 1 - 6 in TSS based on central readers assessment	Summary	FAS	observed data	N/A
	Main analysis	FAS	The data after an intercurrent event, if collected, will be excluded. Missing data will not be imputed.	MMRM with terms treatment, visit, and interaction of treatment and visit
ISGA success and ISGA clear/almost clear at Week 6/EOT based on HVP in-person assessment	Main analysis	FAS	The data after an intercurrent event, if collected, will be excluded, data at Week 6 or EOT will be included.	Normal approximation
ISGA success and ISGA clear/almost clear at Weeks	Main analysis	FAS	A participant with a missing observation or after an	Normal approximation

1- 6 based on central readers assessment			intercurrent event of discontinuation of treatment will be considered a non-responder for the visit of interest	
Percent change from baseline in %BSA at Week 6/EOT based on HVP in-person assessment	Summary	FAS	observed data	N/A
	Main analysis	FAS	The data after an intercurrent event, if collected, will be excluded, data at Week 6 or EOT will be included.	ANOVA with term treatment
Percent change from baseline in %BSA at Weeks 1-6 based on central readers assessment	Summary	FAS	observed data	N/A
	Main analysis	FAS	The data after an intercurrent event, if collected, will be excluded. Missing data will not be imputed.	MMRM with terms treatment, visit, and interaction of treatment and visit

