9.4.3. Secondary Endpoints/Estimands Analysis

Percentage change from baseline in %BSA at Week 6/EOT based on in-person assessment will be analyzed using an ANOVA model that includes treatment group as a factor (see [Section 9.4.1.2](#)) based on Estimand 1 using FAS.

Achievement of an ISGA success and ISGA clear/almost clear at Week 6/EOT based on in-person assessment will be analyzed using the method described in [Section 9.4.1.1](#) using Estimand 1 and FAS.

Percent change from baseline in TSS and %BSA based on Central Readers assessments will be analyzed using MMRM as described in [Section 9.4.1.2](#). Missing data are assumed MAR. Under MAR assumption, MMRM will yield unbiased estimates and valid inferences for treatment effects assuming all participants maintain therapy. This analysis will be based on Estimand 3 using FAS.

Achievement of an ISGA success and ISGA clear/almost clear by time point based on Central Readers assessments will be analyzed using the method described in [Section 9.4.1.1](#). Observations after the discontinuation of study intervention or missing values for any reason will be handled by setting the endpoint to nonresponsive. Note that this is a composite endpoint in the sense that a response requires the participant completes a visit of interest eg, Week 6, and achieves a response per the defined response criteria (otherwise it is considered a nonresponse). This method of handling missing response is known as missing response as non-response (MR-NR). The analysis will be based on Estimand 2 using FAS.

CCI

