4. ANALYSIS SETS (POPULATIONS FOR ANALYSIS)

For purposes of analysis, the following analysis sets are defined:

Population	Description
Screened	All participants who sign the informed consent form (ICF).
Enrolled	All participants who sign the ICF and are not screen failure.
Randomly Assigned to Study Intervention	All participants who are randomized.
Full Analysis Set (FAS)	All participants who are randomly assigned to study intervention and apply at least 1 dose of study intervention. Participants will be analyzed according to the intervention they are randomized. For change from baseline or percent change from baseline endpoints it would require that a participant have a baseline value and at least one post-baseline value to be included in the analysis for that endpoint. For the endpoint with a threshold requirement for change from baseline, only participants with a baseline value \geq the threshold will be included in the analysis.
Safety Analysis Set (SAF)	All participants who are randomly assigned to study intervention and apply at least 1 dose of study intervention. Participants will be analyzed according to the intervention they actually received.
Full Analysis Set-Interim Analysis (FAS-IA)	All participants who are randomly assigned to study intervention and apply at least 1 dose of study intervention and complete 6 weeks treatment or early discontinue study intervention at the IA cutoff date. Participants will be analyzed according to the intervention they are randomized.
Safety Analysis Set-Interim Analysis (SAF-IA)	All participants who are randomly assigned to study intervention and apply at least 1 dose of study intervention and complete 6 weeks treatment or early discontinue study intervention at the IA cutoff date. Participants will be analyzed according to the intervention they actually received.

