5.2.1. Analyses for Continuous Data

Analysis of Variance (ANOVA)/Analysis of Covariance (ANCOVA) for Non-longitudinal Continuous Data:

The non-longitudinal continuous data will be analyzed by ANOVA with treatment as the factor. ANCOVA will be used if relevant baseline value and/or other factors are included as covariates. Comparison of crisaborole ointment, 2%, BID to vehicle (providing LSM of the treatments, LSM of the treatment difference, 1-sided p-value and 90% CI) will be generated.

Mixed Effect Model Repeat Measurement (MMRM) for Longitudinal Continuous Data:

The longitudinal continuous endpoints will be analyzed with MMRM that includes fixed effects of treatment group, visit, and treatment-group by visit interaction, without imputation for missing values. If the endpoint is change from baseline, baseline will be included in the model as a covariate. A common unstructured variance-covariance matrix will be used, provided it converges. If this is a convergence issue, other type of covariance matrix such as first order autoregressive (AR[1]), compound symmetry will be used. Comparison of crisaborole ointment, 2%, BID to vehicle (providing least squares means [LSM] of the treatments, LSM of the treatment difference, 1-sided p-value and 90% CI) at each time point during the first 6 weeks will be generated using this model.

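### The SAP does not settle whether baseline enters the MMRM for Central Reader percent change in TSS and %BSA: Section 5.2.1 has a conditional baseline rule, and Appendix 1 lists the model without baseline

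*SAP*

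**What the plan says.** SAP 5.2.1 describes the model for longitudinal continuous data as an "MMRM that includes fixed effects of treatment group, visit, and treatment-group by visit interaction, without imputation for missing values". It then adds a condition: "If the endpoint is change from baseline, baseline will be included in the model as a covariate". Protocol 9.4.1.2 carries the same rule.

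The two endpoints that use this model are both percent changes. SAP 6.2.5 has "Variable: Percent change from baseline to Weeks 1-6 in TSS based on central readers assessment", and SAP 6.2.7 has "Variable: Percent change from baseline to Week 1- 6 in %BSA based on Central Readers digital images assessment". Neither section lists model terms; each says "Analysis method: MMRM in" and points to 5.2.1. Protocol 9.4.3 does the same: "Percent change from baseline in TSS and %BSA based on Central Readers assessments will be analyzed using MMRM as described in" Section 9.4.1.2.

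SAP Appendix 1 does list terms. For both endpoints the entry is "MMRM with terms treatment, visit, and interaction of treatment and visit". Baseline is in neither row.

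The FAS definition in SAP 4 names the two kinds of endpoint side by side: "For change from baseline or percent change from baseline endpoints it would require that a participant have a baseline value".

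**The concern.** Section 5.2.1 and Appendix 1 both specify the same two secondary analyses, and they agree only if the baseline rule in 5.2.1 does not reach percent change. The SAP does not say whether it does. Two competent programmers could therefore build different models, and these would give different least-squares mean differences, standard errors and p-values.

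Two things are at stake in the choice. The first is precision: if baseline severity is correlated with percent change, the model without baseline has the larger SE. The second is the missing-data argument. SAP 5.3.2 relies on MAR for unbiased MMRM estimates, and MAR is conditional on what the model contains. Participants take the images themselves and the images must pass quality control (Protocol 8.1.3), so some reads may be missing. If that depends on baseline severity, the model with baseline conditions on it directly and the Appendix 1 model does not. The documents do not say that missingness follows this pattern.

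**Working it through.** **Step 1. The two readings.**

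| Reading of the 5.2.1 condition | Model from 5.2.1 | Model in Appendix 1 | Result |
|---|---|---|---|
| Percent change counts as change from baseline | treatment, visit, interaction, baseline | treatment, visit, interaction | Contradiction |
| Percent change does not count | treatment, visit, interaction | treatment, visit, interaction | Agreement, but baseline is left out |

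**Step 2. The planning figure.** The documents give no figure for the Central Reader MMRM. The inputs borrowed here are those of the primary endpoint in Protocol 9.2: difference 22 points, SD 35 points, 35 per arm, one-sided 5%.

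- Unadjusted SE = 35 × √(2/35) = 8.37 points.
- Power = Φ(22/8.37 − 1.645) = 83.8%; with the noncentral t on 68 degrees of freedom it is 83.1%.

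Both agree with the stated power of at least 80%, which is not in dispute.

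**Step 3. Effect of baseline on the SE.** Let r be the correlation of baseline with percent change. It is not in the documents, so a range is shown. For N = 70,

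SE with baseline ÷ SE without = √(1 − r²) × √(1 + 1/66).

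The second factor, 1.0075, is the price of estimating one slope.

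| r | √(1 − r²) | Ratio with slope cost | SE with baseline (points) |
|---|---|---|---|
| 0 | 1.000 | 1.008 | 8.43 |
| 0.1 | 0.995 | 1.003 | 8.39 |
| 0.2 | 0.980 | 0.987 | 8.26 |
| 0.3 | 0.954 | 0.961 | 8.04 |
| 0.4 | 0.917 | 0.923 | 7.73 |
| 0.5 | 0.866 | 0.873 | 7.30 |

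**Step 4. Effect on the estimate.** Under randomisation the two estimates differ only through chance baseline imbalance. The SD of the difference is about r × unadjusted SE: 0.3 × 8.37 = 2.5 points and 0.5 × 8.37 = 4.2 points.

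**Step 5. Simulation check.** A six-visit repeated-measures model with unstructured covariance was fitted to complete simulated data, 35 per arm and SD 35, with 300 data sets per value of r.

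| r | SE without | SE with | Ratio | Mean absolute difference in Week 6 estimate (points) |
|---|---|---|---|---|
| 0 | 8.34 | 8.39 | 1.006 | 0.6 |
| 0.3 | 8.37 | 8.06 | 0.963 | 1.9 |
| 0.5 | 8.32 | 7.28 | 0.875 | 3.5 |

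The ratios match the formula. The check uses complete data, so it does not measure any bias from missing images.

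**The case against.** The strongest reply is that there is no contradiction. The condition names change from baseline, both endpoints are percent changes, and SAP 4 lists the two kinds separately. Read literally, 5.2.1 then gives exactly the Appendix 1 model. The in-person percent-change analyses of TSS and %BSA also have no baseline term, which fits that reading. Nor can one argue that the clause would otherwise be empty. Every visible longitudinal continuous endpoint is a percent change, but endpoint text is blacked out, and SAP 3.4 refers to daily assessed endpoints that are not among the visible ones. The clause may serve those.

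This stands as far as it goes: a firm conflict between two models is not proven. It does not settle the matter. The ANOVA comparison is weak, because covariates are optional in the ANOVA/ANCOVA paragraph of 5.2.1, whereas the MMRM paragraph makes baseline mandatory once its condition is met. SAP 4 shows that the authors could name both kinds when they meant both, but 5.2.1 does not say which it means. And if the narrow reading is right, the plan still leaves out a covariate it already holds.

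A second reply is that Appendix 1 is specific to the endpoint and so gives the analyst a model to follow. That is fair. It answers any suggestion that the model is open to choice after unblinding; nothing in the documents shows such an intention. But the SAP nowhere says that Appendix 1 overrides 5.2.1.

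**Conclusion.** The point holds as an unresolved ambiguity with a better option available. On the broad reading the SAP contradicts itself; on the narrow reading it omits a useful covariate. Either way the two MMRM rows should be changed.

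The gain is modest and depends on an unknown correlation. The SE is practically unchanged at 0 to 0.1, about 4% smaller at 0.3 and about 13% smaller at 0.5. These figures assume that the primary endpoint's SD of 35 points, which Protocol 9.2 bases on atopic dermatitis data, and its 35 per arm carry over to Central Reader scores. The missing-data benefit depends on missing reads being related to baseline severity.

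A reader might infer that the choice of model could move a trial conclusion across the one-sided 5% line. The documents do not support that. SAP 3 calls the Central Reader analyses supportive, Protocol 9.1.2 has no multiplicity scheme, and the hypothesis in SAP 5.1 and the interim criterion in SAP 7 rest on the primary endpoint. The primary ANOVA and the sample size are unaffected.

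**What to change.** Before unblinding:

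- In the two MMRM rows of Appendix 1, add the Central Reader baseline value of the same measure as a covariate, beside treatment, visit and their interaction.
- In SAP 5.2.1, extend the baseline condition to *change or percent change from baseline*, so that 5.2.1, 6.2.5, 6.2.7 and Appendix 1 give one model.

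A baseline-by-visit term is optional; neither document mentions it, and it is not needed to reconcile the sections.

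The cost is a wording edit. The baseline score is already needed to compute the endpoint, so no new data are collected. The statistical price is about one degree of freedom and an SE increase of under 1% if the correlation is zero. SAP 2 lets the SAP modify the protocol's plans and calls for an amendment only for major changes to the primary endpoint or its analysis, so a SAP revision is enough. Protocol 9.4.1.2 can be aligned if the protocol is amended for another reason.
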